## 7.6 Request for CPI-613

CPI-613 must be requested from Cornerstone by the Principal Investigator (or authorized designees). CPI-613 may not be used outside the scope of this protocol, nor can it be transferred or licensed to any party not participating in this clinical study. Cornerstone policy requires that

Comprehensive Cancer Center of Wake Forest University (CCCFWU)  
A Pilot Study of CPI-613 in Patients with Myelodysplastic Syndrome Who Have Failed Previous Therapy  
CCCFWU #29113

CPI-613 be shipped directly to the institution where the patient is to be treated. Cornerstone does not permit the transfer of CPI-613 between institutions (unless with prior written approval from Cornerstone). Requests must be submitted to Cornerstone by fax or email to the following address:

[name]  
Department of Regulatory and Clinical Affairs  
Cornerstone Pharmaceuticals, Inc.  
[name]  
[name]  
[contact]  
Telefax: [contact]  
Email: [[contact]](mailto:[contact])

The following information must be provided in the request of CPI-613 from Cornerstone:

- Names of the principal investigator and the requestor (if different)
- Name of the study site
- Name of the pharmacist responsible for receiving and storing CPI-613
- Name of the person and address where CPI-613 is to be shipped to
- Amount (# vials) requested
- Date of request
- Date shipment expected
- Study Protocol (title and protocol#) for which the requested CPI-613 is to be used

## **7.7 Procurement of Investigational Drug**

Relevant regulations require investigators to establish a record of the receipt, use and disposition of all investigational products. Investigators may delegate responsibility of drug ordering, storage, accountability and preparation to their designees.

The investigator, or the designee, will be responsible for dispensing and accounting of CPI-613 provided by Cornerstone and for exercising accepted medical and pharmacy practices.

Records of inventory, dispensation and disposition (vials received, source and dates) must be maintained. In addition, all doses dispensed should be accounted for by recording the date, study number and name, patient identification, patient initials, patient medical record number and balance forward. These records must be maintained and kept at the study site, and will be reviewed by Cornerstone, or its designee, during periodic monitoring visits.

## **7.8 Disposal of CPI-613**

The following procedures are to be taken in disposal of CPI-613:

- During the study, store the used CPI-613 vials (which must be separate from the unused CPI-613 vials) at room temperature in an access-limited area. Alternatively, destroy the used CPI-613 vials according to institutional policy after documentation of the number of used CPI-613 vials and remaining volume in each used vial.

- At the end of the study, deface the label (both used and unused vials) with a permanent marking pen.
- For used CPI-613 vials (if not already destroyed according to institutional policy), after documentation of the number of used CPI-613 units and remaining volume in each container, the used containers should be destroyed at the site according to the institutional procedures for destroying toxic chemicals. A certificate documenting the destruction of used vials must be kept on file.
- All unused CPI-613 vials must be destroyed according to the policy of the institution. The destruction of CPI-613, and the quantity destroyed, must be documented. A copy of the Certificate of Destruction should be sent to:

[name]  
Department of Regulatory and Clinical Affairs  
Cornerstone Pharmaceuticals, Inc.  
[name]  
[name]  
[contact]  
Telefax: [contact]  
Email: [[contact]](mailto:[contact])

## **7.9 Calculation of the Amount of CPI-613 for Each Patient**

The amount of CPI-613 at each dose level is based on the BSA of the patient. The BSA values will be calculated based on the height and body weight taken during screening and this BSA value is used throughout the study. This is unless there is a >10% change in the body weight from baseline during the study. At that point, BSA should be revised based on the new body weight and height. The new BSA values will be used from that point on for the remainder of the study, unless there is another >10% change in body weight which will require another revision of the BSA.

## **7.10 Concomitant Medications and Prophylactic Treatment**

Patients cannot receive any standard or investigational treatment (except CPI-613) for their cancer, or any other investigational drugs for any non-cancer indications, while on this study. All otherwise permitted concomitant medications (including trade and generic names, dosage and dosing schedule) must be recorded. Treatment of disease-related symptoms (such as nausea) is permitted. Medications administered in such instances will be considered concomitant medications and should be documented accordingly. Supportive treatment may include anti-emetic, anti-diarrhea, anti-pyretic, anti-allergic, anti-hypertensive medications, analgesics, antibiotics, allopurinol, and others such as blood products and bone marrow growth factors. Patients may use erythropoietin for chronic anemia. The treating physician may utilize erythropoietic factors, or blood or platelet transfusions at their discretion.

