## 1.0 BACKGROUND AND STUDY OBJECTIVES

### 1.1 Myelodysplastic Syndrome

Myelodysplastic syndrome (MDS) is a diverse collection of hematological malignancies that involve dysplasia of the stem cells in the bone marrow, resulting in disorderly and ineffective hematopoiesis. The number and quality of blood-forming cells decline irreversibly, further impairing blood production. Patients with MDS often develop severe anemia resulting in susceptibility to infection, bleeding, etc., and require frequent blood transfusions. In most cases, the disease progresses over time and the patient develops cytopenia due to deteriorating bone marrow function. The outlook in MDS is poor, and some patients will progress to Acute Myeloid Leukemia (AML) within a few months. The median survival varies from years to months, depending on the risk level of the disease.

Treatment of MDS is complicated. Although allogeneic bone marrow transplant (BMT) is a potential curative treatment for MDS, a match donor is not always available. Furthermore, most patients with MDS are older and not appropriate candidates for BMT. The prognosis and treatment for MDS vary depending on the patient's International Prognostic Scoring System (IPSS) score (Greenberg et al. 1997). Regardless of risk category, a patient's age and existing comorbidities are also factored into treatment decisions. Patients with a Low/Intermediate-1-Risk score (IPSS 0-1) may live with their disease for a number of years. These patients are primarily treated with low-intensity supportive care, especially red blood cell transfusions, to treat their symptoms and maintain their quality of life. In small subsets of Low/Intermediate-1-Risk MDS patients, hematopoietic cytokines or antithymocyte globulin may reduce transfusion requirements. The drawbacks to these treatments are high failure rates even with improved predictive models, and high cost of cytokines. Patients with higher scores (intermediate-2 and high risk; IPSS  $\geq 1.5$ ) are at higher risk of transformation to AML and many will die from their disease within 1 year of diagnosis. Treatment of these patients is with intensive therapies using hypomethylating agents (decitabine and azacitidine). Unfortunately, these agents induce significant toxicities at therapeutic doses. Furthermore, after relapsing from a hypomethylating agent, there is essentially no effective treatment for this disease. Therefore, additional treatment options for MDS are greatly needed.

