### 2.2 Outcome Measures

The primary outcome measure is to evaluate the response rate (RR) of CPI-613 in these patients. Response rate is defined as the combined rate of complete remission (CR), marrow CR, partial remission (PR), or stable disease (SD) as described by Cheson, et al. (2006).

The secondary outcome measures are:

- Safety
- Progression-free-survival (PFS)
- Overall survival (OS)
- Changes in the frequency of blood transfusion
- Hematologic improvement (HI; as defined by Cheson et al . [2006])

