**Table 5-1: Study Procedures**

Assessments	Pre-study 	Each Treatment Cycle (1 cycle = 4 weeks)					Follow-Up
		Day 1	Day 2	Day 3	Day 4	Day 5	
Medical history	✓						
Physical exam, height, weight, vitals	✓	✓ 					
Pregnancy test	✓						
Evaluation of symptoms and vital signs	✓	✓ 	✓ 	✓ 	✓ 	✓ 	
ECOG performance status and survival	✓	✓ 					
Clinical chemistry, hematology and coagulation 	✓	✓ 					
BMP			✓	✓	✓	✓	
CPI-613 		✓	✓	✓	✓	✓	
Assessment of response 		Cycles 2, 4, 6 (and every 3 cycles thereafter until disease progression)					
Bone marrow exam 	✓	Cycles 3 and 6 (and at the discretion of the physician or if peripheral blood criteria for a complete remission are met (ie ANC>1000, Platelets>100k and freedom from blood transfusions) thereafter until disease progression)					
Survival and post-study follow-up 							✓

CR = Complete Remission; D1 = day 1; D4 = day 4; ECOG = Eastern Cooperative Oncology Group; hr = hour; min = minute; PR = Partial Remission.

 CPI-613 is given as a 2-hr IV infusion via a central venous catheter.

 These tests are performed with results available for review within 24 hrs before administration of the anti-tumor agents.

 Specific chemistry, hematology and coagulation are listed in section 5.2.2. Renal function will be assessed utilizing the Cockcroft-Gault formula.

 Cycles 2, 4, 6 (and every 3 cycles thereafter until disease progression).

 Survival and post-study cancer treatment will be monitored by the treating physician during routine follow-up visits for 5 years or until death.

 CR, marrow CR, and PR will be assessed using hematology results from blood work and bone marrow exam results, according to the criteria described by Cheson et al. (2006).

 Frequency of transfusion is defined as the number of transfusions received during the previous 8 weeks. The baseline assessment should reflect the number of transfusions received in the 8 weeks prior to enrollment. On-treatment assessments should be performed at the end of cycles 2, 4, and 6, and every 3 cycles thereafter until progression)

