### Proposed Analyses

The analyses for this protocol will be primarily descriptive. With a sample size of 20 treated at MTD, we do not expect to see statistically significant effects for the outcomes of interest, however this data will provide useful preliminary data on the overall safety and efficacy of CPI-613 and provide useful data to predict the variability and likely effect sizes for these outcomes.

For the primary outcome, we will present the proportion (along with a 95% confidence interval) of patients who respond. Response rate (RR) is defined as the combined rate of CR, marrow CR, PR, or SD as described by Cheson, et al. (2006). Response criteria are shown in Appendix G. In addition, we will determine the number of patients who achieve HI, and a reduction in transfusion requirements. For the time-to-event outcomes, we will estimate survival curves for OS and PFS using Kaplan-Meier techniques. In addition, we will estimate the 6 month and 1-year OS and PFS rates for these participants. We will also examine toxicities by looking at each toxicity identified earlier in the protocol by grade.

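### Appendix F stops at 10 transfusions and omits what the erythroid rule needs; Section 9 counts HI and transfusion reduction without identifying growth-factor starters

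*Combined protocol and SAP*

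**What the plan says.** Section 2.2 lists five secondary outcomes. Two of them are HI and "Changes in the frequency of blood transfusion". Table 5-1, footnote 7, fixes the measure for the latter: "Frequency of transfusion is defined as the number of transfusions received during the previous 8 weeks".

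Section 10 makes Appendix F the form on which that frequency is documented before entry in REDCap. Its RBC and platelet lines are rows of numbers from 0 to 10, one to be circled. The box marked Other belongs to the time point, not to the count. There is no field for RBC units or for hemoglobin (Hgb).

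Appendix H, Table 4, allows an erythroid response through fewer RBC transfusions: at least 4 fewer per 8 weeks, worded partly in units and partly in transfusions. Pretreatment transfusions count only if given at Hgb of 9.0 g/dL or less. HI itself is ticked on Appendix I and signed by the treating physician and the principal investigator.

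On growth factors, Section 7.10 says "Patients may use erythropoietin for chronic anemia" and "The treating physician may utilize erythropoietic factors, or blood or platelet transfusions at their discretion". It also says "All otherwise permitted concomitant medications (including trade and generic names, dosage and dosing schedule) must be recorded". For the analysis, Section 9 says only that "we will determine the number of patients who achieve HI, and a reduction in transfusion requirements".

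**The concern.** There are two separate gaps.

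**The form.** The outcome is a count over 8 weeks with no upper limit, but the prescribed record has one. A heavily transfused patient can improve or worsen without any change on the form. In addition, the two items needed to apply the erythroid transfusion rule are missing, so an erythroid tick on Appendix I that rests on transfusions cannot be traced back to recorded data.

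**The analysis.** Section 1.1 acknowledges that "In small subsets of Low/Intermediate-1-Risk MDS patients, hematopoietic cytokines or antithymocyte globulin may reduce transfusion requirements", and Section 3.1 admits any risk group, so such patients can enroll. With no control arm (Section 2.3), a count of improved patients does not show how many improved after a growth factor was started or increased. Section 7.10 requires the drug record, but no text uses it in the analysis, and the on-study forms tabulated in Section 10 include none for concomitant medication.

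At stake is the use of these counts as preliminary data on activity and on likely effect sizes, which is the purpose Section 9 gives for the study.

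**Working it through.** **Inputs.** 20 patients in one arm (Sections 6.1 and 2.3); two-sided 95% intervals (Section 9); top of each Appendix F count line, 10; erythroid transfusion threshold, 4 per 8 weeks, and Hgb limit, 9.0 g/dL (Appendix H, Table 4). The documents give neither the number of patients with more than 10 transfusions nor the number of growth-factor starters, so both are assumed below.

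**The plan's own figure.** Section 9 gives no precision for HI or transfusions. Its only figure, 0.22 for the response rate, reproduces as 1.96 × √(0.25/20) = 0.219 and is not disputed here. The intervals below are exact (Clopper-Pearson).

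**Step 1: the cap.** Assume 10 is circled for any higher count. With baseline b and on-treatment count t, recorded fall = min(b,10) − min(t,10).

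| Baseline → on treatment | True fall | Recorded fall |
|---|---|---|
| 14 → 10 | 4 | 10 − 10 = 0 |
| 14 → 7 | 7 | 10 − 7 = 3 |
| 10 → 14 | −4 (a rise) | 10 − 10 = 0 |

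- If b is 10 or less, every fall is recorded correctly.
- If b is 11 or more, the recorded fall is 10 − min(t,10), which is below 4 once t is 7 or more. A true fall of 4 or more is therefore hidden only when b ≥ 11 and t runs from 7 to b − 4.
- Section 9 sets no threshold for a reduction. If any fall counts, it is hidden only when b ≥ 11 and t ≥ 10.
- Over all pairs of b and t from 0 to 20, 55 of the 153 true falls of 4 or more are recorded as less than 4. No false fall is created. These counts describe the grid, not patients.

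**Step 2: the missing items.**

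- Hgb: 6 to 2 transfusions is 6 − 2 = 4 on the form. If one of the 6 baseline transfusions was given at Hgb above 9.0, the rule gives (6 − 1) − 2 = 3, below the threshold. The form reads the same either way.
- Units (assumption: 1 or 2 per transfusion): 2 transfusions to 0 is a fall of 2 × 1 = 2 units or 2 × 2 = 4 units. The form reads 2 to 0 in both cases.

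**Step 3: growth factors.** Assume 4 HI responders, of whom g improved in the affected lineage only after a growth factor was started or increased. Sensitivity count = (4 − g)/20, so each such patient is worth 1/20 = 5 points.

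| g | Count | Rate (exact 95% CI) |
|---|---|---|
| 0 | 4/20 | 20.0% (5.7–43.7) |
| 1 | 3/20 | 15.0% (3.2–37.9) |
| 2 | 2/20 | 10.0% (1.2–31.7) |
| 4 | 0/20 | 0% (0–16.8) |

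The denominator must stay fixed. Dropping 3 non-responding starters (assumed) would give 4/17 = 23.5% (6.8–49.9), a rise caused by the exclusion alone.

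**The case against.** The case on the other side is substantial.

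- **Appendix F matches its own definition.** Footnote 7 asks for a number of transfusions, and no text says HI is derived from this form. That stands for units and Hgb: their absence is a gap in traceability, not a contradiction. It does not excuse the cap, which truncates the very number footnote 7 defines.
- **The cap is conditional.** It needs more than 10 transfusions in 8 weeks and staff who circle 10 instead of writing the number. The REDCap fields are not shown and might accept more. This limits the size of the problem, but the form as printed still invites the loss.
- **The growth-factor effect is probably small.** Section 1.1 adds that "The drawbacks to these treatments are high failure rates even with improved predictive models", and Section 2.1 names growth factors among the agents patients may already have failed. Starters can be found from the Section 7.10 record. All of this stands; what is missing is a rule for using the record.
- **A blunt rule would misclassify.** Counting every responder with any overlapping growth factor as a non-responder would cancel an HI established before the drug began, or a platelet response in a patient given erythropoietin. This is right and shapes the fix.
- **Baseline use is unclear.** Exclusion Q bars biologic agents and other standard cancer treatment in the 2 weeks before CPI-613, without saying whether growth factors are covered. If they are, a patient who resumes one on study would look like a starter. The analysis definition should say how such a patient is classed.

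**Conclusion.** Both gaps are real and modest. Following Appendix F as printed loses information above 10, and the transfusion route to erythroid HI cannot be checked from the forms shown. Section 9 leaves growth-factor starters unidentified in two single-arm counts. The direction of the cap is known (it hides falls and rises and invents no fall), but its frequency is not. The 5 points per reclassified patient is arithmetic; the number of such patients is assumed.

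A reader might infer more than the documents support:

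- That the HI results as a whole are unreliable. The Hgb-rise, platelet and neutrophil routes do not depend on Appendix F.
- That growth factors will account for the improvements seen. Section 1.1 points to small subsets and frequent failure, and no figure for on-study use is given.
- That the main conclusion of the trial is at risk. The primary response rate is little affected, no decision rule depends on HI, and Section 9 describes the analyses as mainly descriptive.

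The change is worth making because it is cheap and best settled before results are seen.

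**What to change.** **(a) Appendix F.** Replace the circled rows with open numeric fields for RBC and platelet transfusions. Record RBC units and the number of RBC transfusions in the period given at Hgb of 9.0 g/dL or less, or use one row per transfusion. A single Hgb value for an 8-week period would not show which transfusions qualify. Cover the 8-week baseline where records allow. State whether the threshold of 4 is in units or in transfusions.

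**(b) Section 9.** Keep the counts over all treated patients as the main result. Report the number of growth-factor starters among responders and among non-responders. Add a sensitivity count over the same denominator. It treats as non-responders only patients whose HI in the lineage affected by the growth factor, or whose reduction in the corresponding transfusion type, began after that growth factor was started or increased. Responses established earlier, or in another lineage, stay as classified. Take drug name, start date and dose changes into the database from the records Section 7.10 already requires.

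**Cost.** A few sentences in Section 9, a revised form, and some extra data entry, most of it for transfusion-level Hgb at baseline. The sensitivity count may understate the study drug where the growth factor did not cause the response. The sample size and permitted care do not change.

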## 8.0 ADVERSE EVENTS LIST AND REPORTING REQUIREMENTS

### 8.1 Adverse Event Characteristics

- **CTCAE term (AE description) and grade:** The CTEP Active Version of the NCI Common Terminology Criteria for Adverse Events (CTCAE 4.0) will be utilized for AE reporting. The CTEP Active Version of the CTCAE is identified and located on the CTEP website at ([http://ctep.cancer.gov/protocolDevelopment/electronic\\_applications/ctc.htm](http://ctep.cancer.gov/protocolDevelopment/electronic_applications/ctc.htm)). All appropriate treatment areas should have access to a copy of the CTEP Active Version of CTCAE.
- **‘Expectedness’:** AEs can be ‘Unexpected’ or ‘Expected’ (see Section 7.1 above) for expedited reporting purposes only.
- **Attribution** of the AE:
  - Definite – The AE is *clearly related* to the study treatment.
  - Probable – The AE is *likely related* to the study treatment.
  - Possible – The AE *may be related* to the study treatment.
  - Unlikely – The AE is *doubtfully related* to the study treatment.
  - Unrelated – The AE is *clearly NOT related* to the study treatment.

#### List of Adverse Events to be Reported:

Abdominal pain  
Alkaline phosphatase  
ALT (SGPT)  
Anorexia  
AST (SGOT)  
Bilirubin (hyperbilirubinemia)  
Calcium (hypercalcemia, hypocalcemia)  
Creatinine  
Diarrhea  
Flushing  
Hemoglobin (anemia)  
Injection site reaction  
Leukocytes  
Lymphopenia  
Nausea  
Neutrophils (neutropenia)  
Platelets (thrombocytopenia)  
Potassium  
Sodium  
Vomiting

All grade 3, 4, 5 adverse events should be reported on flow sheets and in ORIS regardless of whether they are on this list.

Comprehensive Cancer Center of Wake Forest University (CCCFWU)  
A Pilot Study of CPI-613 in Patients with Myelodysplastic Syndrome Who Have Failed Previous Therapy  
CCCFWU #29113

All AEs are described in the Investigator's Brochure, and all of them are considered "expected".

All Serious Adverse Events (SAEs) which are Possibly, Probably or Definitively Related to CPI-613, and Unexpected are required to be reported to Cornerstone Pharmaceuticals via the provided SAE Reporting Form within 7 days. All completed forms must be sent to [name] at Cornerstone. Cornerstone will submit any applicable SAEs to the FDA.

SAE reports must be submitted to Cornerstone by fax or email to the following address:

Department of Regulatory and Clinical Affairs  
Cornerstone Pharmaceuticals, Inc.  
[name]  
[name]  
[contact]  
Telefax: [contact]  
Email: [[contact]](mailto:[contact])

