## 6.2 Dosing Delay and Dose Modification of CPI-613 in the Event of Adverse Events

For adverse events unrelated to serum creatinine elevation or reduction in renal function but are possibly, probably or definitely related to CPI-613, the occurrence of Grade 1 toxicity does not generally require dose modification for subsequent doses for that patient. However, if Grade 2 toxicity (other than diarrhea and nausea) develop, treatment is to be withheld and can resume only after the Grade 2 toxicity has been reduced to Grade 1 or below, and the dose level for subsequent doses for that patient will be reduced by 25%. Grade 2 nausea and diarrhea do not require withholding treatment or dose reduction. If Grade 3 or 4 toxicity related to CPI-613 develops, dosing of CPI-613 of that patient will be withheld and the patient shall be monitored for recovery from, and reversibility of, such Grade 3 or 4 toxicity. To resume treatment with CPI-613 for a patient who has had CPI-613-related Grade 3 or 4 toxicity, the Grade 3 or 4 toxicity must be reduced to Grade 1 or below, and the dose level for subsequent doses for that patient will be reduced by 50%. Patients can be re-dose-escalated at the discretion of their treating physician as long as no recurrence of the toxicity is seen at the reduced dose.

For adverse events related to creatinine elevation or reduction in renal function that are possibly, probably or definitely related to CPI-613, dosing of the patient will be withheld even if the severity level is Grade 1 or above. Treatment can resume only after the toxicity has been reduced to Grade 0. The dose level for subsequent doses for that patient will be reduced by 15% if the severity level is of Grade 1, by 25% for Grade 2 toxicity, and by 50% for Grade 3 or 4 toxicity.

Furthermore, if the toxicity possibly, probably or definitely related to CPI-613 is acute renal failure and the severity level is Grade 3 or 4, further patient enrollment will be temporarily suspended in order to enable assessment of the following aspects of the trial and implementation of corrective measures or protocol amendment, and if necessary:

- compliance of the investigators to the study protocol
- evaluation of the appropriateness of the procedures for monitoring renal function

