## **8.2 STRC SAE Reporting Requirements**

The Safety and Toxicity Review Committee (STRC) is responsible for reviewing SAEs for CCCWFU Institutional studies as outlined in Appendix B. STRC currently requires that all unexpected grade 4 and all grade 5 SAE's on these trials be reported to them for review. This procedure is a part of the CCCWFU Data Safety Monitoring Plan that our institution has on file at the NCI. All CRM staff members assisting a PI in investigating, documenting and reporting an SAE qualifying for STRC reporting are responsible for informing a clinical member of the STRC committee as well as the entire committee via the email notification procedure of the occurrence of an SAE.

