### What is considered an SAE under this mandatory procedure?

Any **unexpected grade 4 event and all grade 5 events** (death during protocol intervention) should be reported. These events should be reported if they occur while a patient is on study treatment or if they occur within 30 days of last study treatment (even if patient begins a new treatment during the 30 days). This window of 30 days should be the standard window to be used in all protocols unless a specific scientific rationale is presented to suggest that a shorter

window can be used to identify events. In addition, if it is not clear whether the Grade 4 is unexpected it should be reported.

**Table 1: Summary of STRC Reporting Requirements for Institutional Pilot, Phase 1, Phase 2 and Phase 3 Interventional Trials**

	ADVERSE EVENT					
	Grade 1, Grade 2, Grade 3		Grade 4		Grade 5	
	Unexpected	Expected	Unexpected	Expected	Unexpected	Expected
Unrelated	Not Required	Not Required	REPORT TO STRC	Not Required	REPORT TO STRC	REPORT TO STRC
Unlikely	Not Required	Not Required	REPORT TO STRC	Not Required	REPORT TO STRC	REPORT TO STRC
Possible	Not Required	Not Required	REPORT TO STRC	Not Required	REPORT TO STRC	REPORT TO STRC
Probable	Not Required	Not Required	REPORT TO STRC	Not Required	REPORT TO STRC	REPORT TO STRC
Definite	Not Required	Not Required	REPORT TO STRC	Not Required	REPORT TO STRC	REPORT TO STRC

STRC reporting may not be appropriate for specific expected adverse events for protocols. In those situations the adverse events that will not require STRC reporting **must be specified in the text of the approved protocol.**

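### Section 8.1 calls all adverse events expected, with no limit on terms or severity, and so undercuts the supplier and safety committee reporting rules that depend on an event being unexpected

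*Combined protocol and SAP*

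**What the plan says.** Section 8.1 first says that an event may be classed as either expected or unexpected, and refers the reader elsewhere for the distinction: "see Section 7.1 above) for expedited reporting purposes only". Section 7.1 describes the drug vial and its contents and says nothing about expectedness.

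Section 8.1 then lists 20 adverse event terms to be reported. It adds that every grade 3, 4 or 5 event goes on the flow sheets and into ORIS, listed or not. The next statement is "All AEs are described in the Investigator's Brochure, and all of them are considered" expected. Immediately after it comes the supplier rule: "All Serious Adverse Events (SAEs) which are Possibly, Probably or Definitively Related to CPI-613, and Unexpected are required to be reported to Cornerstone Pharmaceuticals", with a limit of 7 days. The supplier passes applicable events on to the FDA.

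Section 8.2 sets the committee rule: "STRC currently requires that all unexpected grade 4 and all grade 5 SAE's on these trials be reported to them for review". Appendix B repeats this and sets it out in its Table 1, titled "Summary of STRC Reporting Requirements for Institutional Pilot, Phase 1, Phase 2 and Phase 3 Interventional Trials". The appendix adds two qualifications. A grade 4 event whose expectedness is in doubt is to be reported. And while it accepts that "STRC reporting may not be appropriate for specific expected adverse events for protocols", it requires any such exempt events to be named in the approved protocol.

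**The concern.** A rule that turns on whether an event is unexpected works only if some events can be unexpected and staff can tell which. Section 8.1 appears to remove the category just before relying on it, and its one pointer to a definition leads to the wrong place. The list is headed as events to be reported, not as expected events, so the heading does not settle how far the statement reaches.

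At stake is prompt outside review of serious toxicity in a 20-patient, open-label, single-arm pilot of a drug whose human toxicity Section 7.2 describes as incompletely understood. The supplier route is the path to the FDA that Section 8.1 describes. The STRC can suspend the trial, but it acts on what is reported to it.

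**Working it through.** No arithmetic on sample size or event rates applies. The check takes each reporting rule and asks which events satisfy it under the two possible readings of the statement in Section 8.1.

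**Inputs**

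- Supplier trigger (Section 8.1): serious, related at least possibly, and unexpected. There is no exception for deaths.
- STRC trigger (Section 8.2, Appendix B): grade 4 if unexpected or if expectedness is unclear; grade 5 always.
- Other routes: ORIS and flow sheets take all grade 3 to 5 events (Section 8.1). The IRB route covers unanticipated problems and adverse events under institutional policy (Section 8.3). Neither uses the label from Section 8.1.

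**Literal reading: every adverse event is expected**

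1. The set of unexpected events is empty. The supplier trigger requires membership of that set, so no serious event qualifies, whatever its grade or attribution.
2. Table 1 of Appendix B has 15 cells that call for a report to the STRC: 5 attribution levels for each of grade 4 unexpected, grade 5 unexpected and grade 5 expected (5 + 5 + 5 = 15). The 5 grade 4 unexpected cells cannot be reached through the label. Grade 4 expected is marked as not required at all 5 attribution levels.
3. Deaths still reach the STRC through the 5 grade 5 expected cells. Grade 4 events reach it only where staff judge expectedness unclear.

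**Narrow reading: only the 20 listed terms are expected**

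1. Unlisted events can be unexpected, so both triggers work for them.
2. Listed terms are expected. The list gives terms without grades, so creatinine, bilirubin or potassium is expected at grade 4 just as at grade 1. Such an event fails the supplier test and, unless its expectedness is judged unclear, falls in the not-required column for the STRC.

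| Route | Literal reading | Narrow reading |
|---|---|---|
| Supplier, related serious events | None qualify, fatal ones included | Unlisted qualify; listed do not, at any grade |
| STRC, grade 4 | Only if expectedness is unclear | Unlisted qualify; listed only if expectedness is unclear |
| STRC, grade 5 | All | All |
| ORIS and flow sheets, grades 3 to 5 | All | All |
| IRB | Unaffected | Unaffected |

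The statement therefore conflicts with the definition above it on the first reading, and leaves a gap in severity on the second.

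**The case against.** The strongest reply is that the narrow reading is the natural one. The statement closes a block devoted to the list, no brochure could describe every conceivable event, and the literal reading would void the definition above it, the supplier rule below it and the STRC's grade 4 rule. Reading the statement as covering the listed terms reconciles all three. That reading is plausible and may well be what the authors meant. But the text does not say so, and the preceding sentence expressly concerns events on or off the list. The severity gap remains even if the reply is accepted.

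A second reply is that Appendix B protects the STRC route. It sends doubtful grade 4 events to the committee, tells staff to apply only its own rules, and wants exemptions named specifically. This stands in part. The contradiction inside Section 8.1 is itself a source of doubt, and a blanket statement arguably does not name specific exemptions. A reader might infer that no grade 4 event would ever reach the STRC; the documents do not support that. Appendix B offers no such protection for the supplier route.

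A reader might also infer that severe renal failure would go unreported. Section 6.2 has its own rule, "if the toxicity possibly, probably or definitely related to CPI-613 is acute renal failure and the severity level is Grade 3 or 4", but that rule suspends enrolment for assessment and neither creates nor removes a report to the STRC or supplier. Acute renal failure is not a listed term, so on the narrow reading the statement does not make it expected. The documents give no ground for treating it as a separate reporting gap.

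Finally, the ORIS and IRB routes continue. That limits the consequence, but recording in ORIS is not expedited review, and the IRB is not the supplier or the STRC.

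**Conclusion.** The concern holds as a contradiction within Section 8.1 and between it and the rules that depend on it. Its size depends on the reading. Literally, the supplier trigger is empty, deaths included, and STRC review of grade 4 events rests on the doubt clause alone. Narrowly, the gap is confined to the 20 listed terms, which are exempt from the supplier rule at every grade and from the STRC grade 4 rule wherever their status is taken as clear. On neither reading is safety reporting as a whole disabled.

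The conclusion rests on the protocol text. The Investigator's Brochure and the safety background in Section 1.2.2 were not available for this check, so whether either gives severities for the listed terms is unknown. The contradiction and the wrong cross-reference do not depend on them. Nothing here shows that any event has actually gone unreported.

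**What to change.** Replace the statement in Section 8.1 with a rule that only the listed terms are expected, and only up to the nature and severity described in the Investigator's Brochure. Any other event, or a listed event of greater severity, is unexpected for both supplier and STRC reporting. Change the pointer to Section 7.1 so that it leads to the list in Section 8.1.

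The cost is a short wording amendment and somewhat more paperwork for serious events. How much more depends on the severities in the brochure: listed terms described there at high grade would remain expected at that grade. No treatment rule, endpoint or analysis changes.
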